4.6.6.11. Renal Safety

Because severe GI events may lead to dehydration, which could cause a deterioration in renal function including acute renal failure, dehydration events will be analyzed. Acute renal events associated with chronic renal failure exacerbation will also be captured. The detailed search criteria can be found in Appendix 1. The listings of TE renal and TE dehydration events will be provided.

Two shift tables examining renal function will be created. A min-to-min shift table of eGFR estimated by the Chronic Kidney Disease Epidemiology Collaboration and Bedside Schwartz equations with unit mL/min/1.73 m², using categories ($<30, \ge30$ to $<45, \ge45$ to $<60, \ge60$ to <90, and ≥90 mL/min/1.73 m²). A max-to-max shift table of UACR, using the categories UACR <30 mg/g, 30 mg/g \le UACR ≤300 mg/g, UACR ≥300 mg/g (respectively, these represent normal, microalbuminuria, and macroalbuminuria).

Descriptive summaries of eGFR by treatment and by nominal visit will be provided for the baseline (with respect to the treatment period) and postbaseline values as well as the change from baseline values. An MMRM as described in Section 4.1.5.4 will be used to fit the changes from baseline in eGFR at all scheduled postbaseline visits using SS1 for double-blind period and using SS2 for overall study (double-blind, open-label, and follow-up periods).

Glomerular hyperfiltration is defined as eGFR >126.8 mL/min/1.73 m² using Zappitelli equation as below:

```
SI units  \begin{aligned} \mathsf{GFR}\;(\mathsf{mL/min}/1.73\;\mathsf{m}^2) &= (507.76\times\mathsf{e}^{0.003\times\mathsf{height}})/(\mathsf{CysC}^{0.635}\times\mathsf{SCr}^{0.547}\;[\mu\mathsf{mol/L}]) \\ \mathsf{If}\;\;\mathsf{renal}\;\;\mathsf{transplant}, \times 1.165 \\ \mathsf{If}\;\;\mathsf{spina}\;\;\mathsf{bifida}, \times (\mathsf{SCr}^{0.925}\;[\mu\mathsf{mol/L}])/40.45 \\ \mathsf{GFR}\;\;= (43.82\times\mathsf{e}^{0.003\times\mathsf{height}})/(\mathsf{CysC}^{0.635}\times\mathsf{SCr}^{0.547}\;[\mathsf{mg/dL}]) \\ \mathsf{If}\;\;\mathsf{renal}\;\;\mathsf{transplant}, \times 1.165 \\ \mathsf{If}\;\;\mathsf{spina}\;\;\mathsf{bifida}, \times 1.57\times\mathsf{SCr}^{0.925}\;(\mathsf{mg/dL}) \end{aligned}
```

The glomerular hyperfiltration status shift from baseline to postbaseline will be summarized at Week 30 using SS1 and at Week 52 using SS2.

The MMRM analyses, based on the subset of participants with or without glomerular hyperfiltration at baseline, will be conducted for eGFR with Zappitelli equation using SS1 for double-blind period and using SS2 for overall study.

Descriptive summaries of UACR by treatment will be provided for the baseline at Week 30 as well as the change from baseline values. An ANCOVA model, as described in Section 4.1.5.4 without imputing any missing data, will be used to fit the changes from baseline in the logarithm of UACR using SS1 for double-blind period and using SS2 for overall study.

Albuminuria: There might be incidences of new albuminuria or worsening of an existing albuminuria. They are defined as follows:

- Incidence of new albuminuria: A new AE of albuminuria (or equivalent term) reported, or at least 1 measurement of UACR ≥30 mg/g after baseline measured by central laboratory in an individual with normal UACR at baseline.
- Worsening of existing albuminuria: A new AE of albuminuria (or equivalent term) with worsening severity compared to previous MH or AE, or a shift in severity category (mild: UACR 1 to 29, moderate:30 to <300, severe ≥300 mg/g) compared to baseline.

To examine AEs of albuminuria for any suggestion of decrease in renal function, summary of acute renal failure searched by MedDRA SMQ, including incidence of new or worsening of albuminuria will be presented by treatment arm, using SS1 from baseline to Week 30 and using SS2 from baseline to Week 52. The AE of albuminuria will be searched using narrow PTs in *Proteinuria* SMQ (20000220).

4.6.6.12. Metabolic Acidosis, Including Diabetic Ketoacidosis

Metabolic acidosis, including diabetic ketoacidosis will be captured as AESIs. The AE database will be searched using MedDRA PT to identify events consistent with metabolic acidosis, including diabetic ketoacidosis. The incidence of the resulting TEAEs will be summarized by treatment and PT using SS1 from baseline to Week 30 and using SS2 from baseline to safety follow-up (Information regarding searching criteria can be found in Appendix 1).

4.6.6.13. Dyslipidemia

An incidence of new dyslipidemia is defined by 1 of the following 2 conditions:

- a new AE of dyslipidemia reported, or
- at least 2 consecutive values of LDL ≥130 mg/dL or fasting TG ≥150 mg/dL on separate visits after randomization measured by central laboratory in an individual with normal LDL and TG at baseline.

The worsening of an existing dyslipidemia is defined by one of the following conditions:

- AE of dyslipidemia with worsening severity compared to previous MH or AE reported, or
- at least 2 consecutive values of LDL ≥130 mg/dL or fasting TG ≥150 mg/dL on separate visits after randomization measured by central laboratory in an individual with previous history of dyslipidemia and normal LDL and TG at baseline, or
- at least 2 consecutive values of LDL or fasting TG at least 5 mg/dL above baseline on separate visits after randomization measured by central laboratory in an individual with LDL ≥130 mg/dL or TG ≥150 mg/dL at baseline.

The incidence of new or worsening of dyslipidemia will be summarized by treatment, using SS1 from baseline to Week 30, and using SS2 from baseline to Week 52. The AE of dyslipidemia will be searched using narrow PTs in *Dyslipidaemia* SMQ (20000026).

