#### Visit 17 Clinic Visit

Clinic visit procedures are like those in the double-blind period EXCEPT fasting is not required at this visit.

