 To compare 5 mg, and 10 mg tirzepatide QW, analyzed as pooled and separate treatment arms, to placebo at 30 weeks, and To assess the effect of 5 mg and 10 mg tirzepatide QW, analyzed as pooled and separate treatment arms at 52 weeks 	 Incidence of new or worsening of dyslipidemia Incidence of new or worsening of hypertension Incidence of new or worsening of albuminuria Incidence of new or worsening of diabetic neuropathy Incidence of new or worsening of diabetic retinopathy or diabetic maculopathy in either eye 	
To assess safety of 5 and 10 mg tirzepatide QW, analyzed as pooled and separate treatment arms, at 30 weeks and through end of the safety follow-up period	 Treatment-emergent adverse events Discontinuation of study intervention due to AEs Adjudicated pancreatic AEs Serum calcitonin Incidence of allergic, hypersensitivity reactions, and injection site reactions Incidence of treatment-emergent anti-drug antibodies to tirzepatide Percentage change from baseline for serum lipid levels Change in systolic and diastolic blood pressure and heart rate from baseline Occurrence of hypoglycemic events Incidence of initiation of rescue therapy for severe-persistent hyperglycemia 	
 To compare 5 and 10 mg tirzepatide QW, analyzed as pooled and separate treatment arms, to placebo at 30 weeks, and To assess the effect of 5 and 10 mg tirzepatide QW, analyzed as pooled and separate treatment arms, at 52 weeks or end of the safety follow-up period 	 Change from baseline for physical and developmental measures height height SDS and weight SDS height velocity Tanner Staging 	
Characterize the pharmacokinetics and pharmacodynamic relationships of tirzepatide	Relationship between tirzepatide exposure and key safety and efficacy measures	
To assess the effect of 5 and 10 mg tirzepatide QW, analyzed as pooled and separate treatment arms, on patient-reported outcomes at 30 and 52 weeks	 Change from baseline for PedsQL Generic Core Scales PedsQL (3.2) Diabetic Module from baseline 	

Objectives	Endpoints
Tertiary/Exploratory	
 To compare 5 mg and 10 mg tirzepatide QW, analyzed as pooled and separate treatment arms, to placebo at 30 weeks, and To assess the effect of 5 mg and 10 mg tirzepatide QW, analyzed as pooled and separate treatment arms, at 52 weeks 	 Incidence of HbA1c ≤6.5% without clinically significant (blood glucose <54 mg/dL) or severe hypoglycemia Incidence of HbA1c <7.0% without clinically significant (blood glucose <54 mg/dL) or severe hypoglycemia

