High and Low ranges will be derived based on age at the time of assessment.

Hypertension: There may be an incidence of new hypertension, or the worsening of an existing hypertension. Following are the definitions of the 2 categories.

An incidence of new hypertension is defined as one of the following:

- A new AE of hypertension reported, or
- at least 2 consecutive measurements of elevated BP (BP ≥95th percentile for age, sex, and height, or SBP ≥130 mmHg and/or DBP ≥80 mmHg) on separate visits after baseline in an individual with normal BP at baseline.

A worsening of an existing hypertension is defined as one the following:

 AE of hypertension with worsening severity compared to previous MH or AE reported, or

- at least 2 consecutive measurements of elevated BP (BP ≥95th percentile for age, sex, and height, or SBP ≥130 mmHg and/or DBP ≥80 mmHg) on separate visits after baseline in an individual with previous history of hypertension and normal BP at baseline, or
- at least 2 consecutive measurements of elevated BP above baseline (at least 7 mmHg for SBP and 5 mmHg for DBP) on separate visits after baseline in an individual with elevated BP (BP ≥ 95th percentile for age, sex, and height or SBP ≥130 mmHg and/or DBP ≥80 mmHg) at baseline.

The AE of hypertension will be searched using narrow PTs in Hypertension SMQ (20000147). Summary of incidence of new or worsening of hypertension by treatment will be provided from baseline to Week 30 using SS1 and from baseline to Week 52 using SS2.

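### The worsening-dyslipidemia rule (SAP 4.6.6.13) counts a 5 mg/dL rise in a lipid that was and stays normal, if the other lipid was raised at baseline

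*SAP*

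**What the plan says.** SAP 1.1 lists "Incidence of new or worsening of dyslipidemia" among the additional secondary endpoints, which are outside type I error control. The objective is to compare the tirzepatide arms with placebo at Week 30 and to describe them at Week 52. SAP 4.6.6.13 adds: "The incidence of new or worsening of dyslipidemia will be summarized by treatment, using SS1 from baseline to Week 30".

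Apart from adverse event reports, SAP 4.6.6.13 has two kinds of laboratory rule:

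- **Both lipids normal at baseline** (the rule for new dyslipidemia, and the second worsening bullet for a child with a history): "at least 2 consecutive values of LDL ≥130 mg/dL or fasting TG ≥150 mg/dL on separate visits after randomization".
- **A raised lipid at baseline** (the third worsening bullet): "at least 2 consecutive values of LDL or fasting TG at least 5 mg/dL above baseline on separate visits after randomization", applied "in an individual with LDL ≥130 mg/dL or TG ≥150 mg/dL at baseline".

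The Protocol's Schedule of Activities places the lipid panel at Week 0 and then at Weeks 8, 16 and 30, all fasting visits. Weeks 42 and 52 follow in the open-label period.

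**The concern.** The third bullet joins two separate either/or conditions. The first decides who is eligible (LDL or TG raised). The second decides what counts as an event (LDL or TG up by 5). No wording links the two, and the post-baseline value need not reach any cut-off. A child can therefore be classed as having worsening dyslipidemia through a lipid that was never abnormal.

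The rule also conflicts with the rest of its own section. The same change in LDL is an event in one child and not in another, and the only difference between them is baseline TG.

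What is at stake is how a reported incidence is read. If a large share of the events are visit-to-visit variation, some of it in a normal lipid, the percentage in every arm is too high to be taken as the rate of worsening dyslipidemia.

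**Working it through.** **Step 1: the wording, with one LDL course applied to two children (mg/dL).**

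| | Baseline TG | Baseline LDL | LDL at Weeks 8 and 16 | Rule that applies | Event? |
|---|---|---|---|---|---|
| Child A | 180 | 80 | 85, 85 | third worsening bullet: 85 − 80 = 5, twice | yes |
| Child B | 120 | 80 | 85, 85 | must reach LDL 130 or TG 150 twice | no |

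This step needs no assumption.

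**Step 2: how often one stable lipid meets the 5 mg/dL rule by Week 30.** The plan states no expected rate or variability for this endpoint, so there is no figure to reproduce. There are three post-baseline values (Weeks 8, 16 and 30). Let the true level be constant and the visit error be normal with SD σ, and let b be the error in the baseline value. Each later value exceeds baseline + 5 with probability p(b) = 1 − Φ((b + 5)/σ). The chance of at least two consecutive exceedances out of three is 2p² − p³, averaged over b.

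| σ (mg/dL) | 3 | 5 | 8 | 10 | 12 | 15 |
|---|---|---|---|---|---|---|
| Chance counted | 6% | 16% | 24% | 27% | 29% | 32% |

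As σ grows, p becomes uniform on 0 to 1 and the chance tends to 2/3 − 1/4 = 41.7%.

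**Step 3: both lipids, in children eligible for the third bullet, with no true change.** This is a simulation. Every distributional input is an assumption:

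- LDL between children: mean 100, SD 27 mg/dL.
- TG between children: median 130 mg/dL, log-SD 0.45.
- Within-child LDL SD 5 to 12 mg/dL and TG coefficient of variation (CV) 10 to 30%.
- Both values of a consecutive pair must be the same lipid. The SAP does not say so, and allowing mixed pairs would add events.

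Selecting on a raised baseline builds in regression to the mean. Under these inputs 46 to 49% of children are eligible.

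| LDL SD, TG CV | Current rule | Rise counted only in a raised lipid | That, plus a normal lipid reaching 130/150 twice (the fix) |
|---|---|---|---|
| 5, 10% | 39.0% | 25.6% | 27.3% |
| 8, 20% | 44.7% | 24.9% | 27.7% |
| 10, 20% | 46.7% | 24.9% | 28.1% |
| 12, 30% | 47.1% | 22.3% | 26.4% |

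The fix removes 1 − 27.3/39.0 = 30% to 1 − 26.4/47.1 = 44% of the false counts. If the two variabilities do not move together, the results shift a little: SD 5 with CV 30% gives 38% falling to 24%, and SD 12 with CV 10% gives 47% falling to 29%. Among children with only TG raised, 15 to 25% are counted through LDL although LDL never reaches 130.

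**Step 4: are true effects lost?** The population is the same, with LDL SD 8 and TG CV 20%. The effect sizes are assumed, and 14 placebo against 28 tirzepatide children are taken as eligible for illustration (Fisher's exact test, two-sided 5%).

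| Assumed true effect | Current rule, stable to affected | Power | Fix, stable to affected | Power |
|---|---|---|---|---|
| Benefit: LDL −5%, TG −20% | 45% to 16% | 42% | 28% to 6% | 42% |
| Harm: LDL +10%, TG +20% | 45% to 83% | 65% | 28% to 64% | 58% |

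The current rule still shows both effects. On the ratio scale harm looks smaller under the current rule (83/45 = 1.8) than under the fix (64/28 = 2.3). On the difference scale it does not (38 against 36 points).

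**The case against.** Four points deserve an answer.

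- **The endpoint is one summary among several.** A reader might infer that false counts hide lipid harm or benefit. The documents do not support that. SAP 4.6.3 fits an MMRM to log-transformed LDL and TG at each scheduled visit, SAP 1.1 lists percentage change in serum lipids as its own endpoint, and SAP 4.6 compares treatment-emergent high and low laboratory values. Step 4 shows that the composite itself still separates the arms. This objection stands in full and limits the point to misclassification and inflated incidence.
- **A sensitive screen is defensible.** Worsening is defined for the child, so a sustained LDL rise in a child with high TG might be wanted as a signal. SAP 4.6.4 uses the same pattern for hypertension: a small fixed increment, twice in a row, in those already raised. That explains an increment rule. It does not explain why the same LDL change is ignored in Child B. The hypertension rule also sets an increment for each measure ("at least 7 mmHg for SBP and 5 mmHg for DBP"), whereas the lipid rule uses one figure for two analytes.
- **A linked reading may have been intended.** It is not written, and code follows the text.
- **The percentages rest on assumed variability.** True. At a within-child SD of 3 mg/dL a single lipid would be counted only 6% of the time. The rule also applies only to children with a raised baseline lipid and needs two consecutive values, so the percentages do not describe all randomized children.

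**Conclusion.** The third worsening bullet is wrong as written. It classes a child as worsened through a lipid that was and stays normal, and it contradicts the cut-off rule that the same section applies to children with both lipids normal. That follows from the text alone.

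The size is conditional on Step 3. About 39 to 47% of stable children with a raised baseline lipid would be counted by Week 30, and about 26 to 28% under the fix. The unlinked wording therefore explains part of the false counts. The rest come mainly from requiring only a 5 mg/dL rise over a single baseline value.

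The consequence is moderate: inflated incidence in an additional secondary endpoint, with no bearing on the primary HbA1c analysis.

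A reader might also infer that 5 mg/dL should give way to a margin taken from the blinded pooled within-child SD. The documents do not support that step. Only one lipid panel is scheduled before treatment, so a pooled SD would mix treatment change with noise, and nothing in the plan indicates what multiple of it to use.

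**What to change.** Reword the third worsening bullet of SAP 4.6.6.13 so that, in a child with LDL of at least 130 or TG of at least 150 mg/dL at baseline, worsening by laboratory value requires one of the following:

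1. Two consecutive post-randomization values at least 5 mg/dL above baseline, in a lipid that was itself at or above its own cut-off at baseline.
2. For a lipid below its cut-off at baseline, two consecutive values of at least 130 mg/dL (LDL) or 150 mg/dL (fasting TG).

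State also that both values of a pair must be the same lipid. Say how consecutive is read for fasting TG across Week 42, where the Protocol notes: "Clinic visit procedures are like those in the double-blind period EXCEPT fasting is not required at this visit".

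The cost is SAP wording and derivation code. No visit, sample or treatment changes. Fewer events will be counted, and the screen for harm becomes slightly less sensitive (power 65% falling to 58% in the Step 4 illustration).

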4.6.6.14. Diabetic Neuropathy

There may be an incidence of new diabetic neuropathy reported, or the worsening of an existing one. Incidence of a new diabetic neuropathy, or equivalent term, will be identified by a new AE of diabetic neuropathy reported. A worsening of diabetic neuropathy is an AE of diabetic neuropathy with worsening severity compared to previous MH or AE. The incidence of new or worsening of diabetic neuropathy will be summarized by treatment with PT, using SS1 from baseline to Week 30, and using SS2 from baseline to Week 52 (information regarding searching criteria can be found in Appendix 1).

4.6.6.15. Major Depressive Disorder/Suicidal Ideation

Severe and serious major depressive disorder/suicidal ideation or behavior will be considered as AESI. The AE database will be searched using SMQs to identify events consistent with major depressive disorder or suicidal ideation (information regarding searching criteria can be found in Appendix 1). The incidence of the resulting TEAEs will be summarized by treatment and PT using SS1 from baseline to Week 30 and using SS2 from baseline to safety follow-up.

4.6.7. Product Complaints

A summary of all product complaints, inclusive of device product complaints that lead to an AE and/or SAE will be included by category.

4.7. Other Analyses

4.7.1. Pubertal Progression Evaluation

These analyses will be guided by the safety estimand. A shift table will be presented in those pubertal patients at baseline (Visit 3) to evaluate the change in Tanner Staging from baseline to last post baseline during double-blind period using SS1 and from baseline to last post baseline during overall study (double-blind period and open-label period) using SS2 for male and female groups and each treatment group without pooling. This includes no change and an increase in 1, 2, 3, and 4 levels. Tanner staging will be performed at baseline, Week 16, Week 30, and Week

52. Participants who have reached Tanner level 5 will not be evaluated again. More details about Tanner Staging are in Section 10.9 of Appendix 9 in Protocol GPGV.

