# Developmental and reproductive safety

Developmental risks in the pediatric and adolescent population will be monitored by regular height and weight measurements and Tanner staging (Section 1.3).

To mitigate possible reproductive risks, pregnant or lactating females are excluded from the study.

Effective contraception use will be discussed regularly with males who have reached puberty and are sexually active, and with females of childbearing potential (Section 10.4.2).

Menstrual cycle reviews and regular pregnancy testing (Section 8.2.4) will also occur for females of childbearing potential. For females who entered the study at prepubertal state, physical exams with Tanner

Staging, time of menarche and menstrual cycle reviews throughout the study period will help monitor for transition to childbearing potential state (Appendix 9, Section 10.9).

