#### Age

1. Participant must be 10 to <18 years of age, at the time of signing the informed consent/assent.

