#### Sex

5. Male or female

Contraceptive use by men or women of childbearing potential should be consistent with local regulations regarding the methods of contraception for those participating in clinical studies. See Appendix 4, Section 10.4 for guidance.

- a. Male participants who have reached puberty are required to use contraception, if sexually active, in compliance with specific local government study requirements (see Appendix 4, Section 10.4 for contraceptive requirements)
- b. Female participants:
  - Are not of childbearing potential, defined as not having reached puberty (see Appendix 4, Section 10.4)

OR

- Are of childbearing potential (see Appendix 4, Section 10.4):
  - Are not breastfeeding.

• Must test negative for pregnancy prior to initiation of treatment as indicated by a negative serum pregnancy test at Visit 1, followed by a negative urine pregnancy test within 24 hours prior to study intervention exposure.

• If sexually active, there must be agreement to use two effective contraceptive methods that include one highly effective method (less than 1% failure rate) for the entirety of the study plus 30 days.

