# 8.2.3. Assessment of Pubertal Progression – Tanner Staging

Participants' pubertal progression will be assessed throughout the study. Tanner staging will be performed at baseline, Week 16, Week 30 and Week 52. Participants who have reached Tanner stage 5 will not be evaluated again. (see Appendix 9, Section 10.9 for Tanner Stages).

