#### **Boys: Development of external genitalia**

Stage 1: Prepubertal

Stage 2: Enlargement of scrotum and testes; scrotum skin reddens and changes in

texture

Stage 3: Enlargement of penis; further growth of testes

Stage 4: Increased size of penis; testes and scrotum larger, scrotum skin darker

Stage 5: Adult genitalia

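### The SAP's only Tanner progression table is restricted to participants already pubertal at baseline, yet lists a 4-level rise that only a prepubertal child could have

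*SAP*

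**What the plan says.** SAP section 4.7.1 plans one progression analysis, under the safety estimand: "A shift table will be presented in those pubertal patients at baseline (Visit 3) to evaluate the change in Tanner Staging". It runs from baseline to the last post-baseline stage, once for the double-blind period (SS1) and once for the double-blind and open-label periods together (SS2). It is split by sex and by treatment group, without pooling the groups. On the categories it says: "This includes no change and an increase in 1, 2, 3, and 4 levels". It adds: "Participants who have reached Tanner level 5 will not be evaluated again". Protocol section 8.2.3 has the same rule, "Participants who have reached Tanner stage 5 will not be evaluated again", and schedules staging at baseline and Weeks 16, 30 and 52.

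Other places bear on who should be in the table:

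- Protocol Appendix 9 (section 10.9) opens the boys' genital scale with "Stage 1: Prepubertal" and gives stage 1 the same label for girls' breast development and for pubic hair.
- Protocol section 5.1 sets the age range ("Participant must be 10 to <18 years of age") and admits girls who "Are not of childbearing potential, defined as not having reached puberty".
- SAP section 1.1 lists Tanner staging among the developmental measures assessed as change from baseline, with no limit by pubertal status.
- SAP Appendix 3 (Table GPGV.6.1) tabulates baseline stage as G1 to G5 for boys and B1 to B5 for girls.

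**The concern.** The population wording and the category list describe different tables. One programmer could drop everyone at stage 1 and leave the 4-level category empty. Another could infer from that category that stage 1 children belong and keep them. The SAP does not say which is right.

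The choice matters because the move from stage 1 to stage 2 or higher can be seen only in children who start at stage 1. If the restriction is applied as written, a paediatric developmental endpoint that section 1.1 states for the whole study population is not reported for the children who had not yet entered puberty.

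**Working it through.** No sample size, alpha or power figure is involved. The check is a count of possible shifts, followed by a search for any other analysis that would cover onset.

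**Inputs.** The scale runs from 1 to 5 (Protocol Appendix 9). Stage 1 is prepubertal, so pubertal means stage 2 or higher. The largest rise listed is 4 levels (SAP 4.7.1).

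**Formula.** Largest possible rise = 5 − baseline stage.

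| Baseline stage | Largest rise | Possible shifts (no change or rise) |
|---|---|---|
| 1 | 5 − 1 = 4 | 0, 1, 2, 3, 4 |
| 2 | 5 − 2 = 3 | 0, 1, 2, 3 |
| 3 | 5 − 3 = 2 | 0, 1, 2 |
| 4 | 5 − 4 = 1 | 0, 1 |
| 5 | 5 − 5 = 0 | none scheduled; not re-staged |

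**Result.** With the population as worded (stage 2 or higher), the shifts are 0 to 3, and the SAP's 4-level category cannot be reached. With stage 1 included, they are 0 to 4, which is exactly the SAP's list.

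**Is onset covered elsewhere?**

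- SAP Appendix 3 gives baseline stage only.
- SAP section 4.6.4 analyses height, height velocity and their standard deviation scores without a pubertal restriction, but these measure growth, not pubertal stage.
- The protocol's Schedules of Activities include menstrual history review, but the SAP has no analysis of menarche.

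No SAP analysis therefore covers entry into puberty.

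**Are the data available?** Yes. The schedule in Protocol section 8.2.3 applies to everyone below stage 5. The gap is in the analysis, not in the collection.

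**How many children?** The documents do not say. A minimum age of 10, a minimum weight of 50 kg and a BMI above the 85th percentile (Protocol 5.1) make a small number plausible. With the planned minimum of 90 participants in three arms, split by sex, the average cell holds 90 / (3 × 2) = 15 participants across all stages. The stage 1 rows would hold a part of that.

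**The case against.** The best answer is that the SAP shows its own intent. A 4-level category makes sense only if stage 1 children are in the table, the endpoint in section 1.1 is unrestricted, and Appendix 3 lists G1 and B1. On this view the word pubertal is a drafting slip and nobody will be left out. That is a plausible reading, and it is why the point is put as a contradiction and not as a settled decision to exclude. It does not remove the need for a correction: the only explicit statement of the table's population is the restrictive one.

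A second answer is that little is lost. Stage 1 numbers may be close to a listing, the placebo-controlled window is 30 weeks, the endpoint is not controlled for type I error, and SAP section 4.1 permits further analyses without amendment. The first three limit what the table can show, and they stand. The permission for extra analyses does not cure a stated exclusion, because it commits nobody to the missing rows.

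A reader might draw two stronger conclusions, which the documents do not support:

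- **Stage 5 participants dilute the progression rate.** Those at stage 5 at baseline are not re-staged, so they have no scheduled post-baseline value, and section 4.7.1 states no pooled denominator. The laboratory shift tables in SAP section 4.6.3 are laid out within baseline category; on that layout stage 5 would be its own row and could not affect stages 2 to 4. No size can be put on any dilution.
- **The protocol names delayed puberty as a treatment risk.** Its text on developmental and reproductive safety (section 2.3.1) speaks of developmental risks in general. The sentence beginning "For females who entered the study at prepubertal state, physical exams with Tanner" goes on to give its purpose as detecting the transition to childbearing potential. It shows that prepubertal entrants are expected; it does not name delayed onset.

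**Conclusion.** The inconsistency in SAP section 4.7.1 is certain on the text: the stated population allows a rise of at most 3 levels and the stated categories go to 4. If the population wording is followed, every stage 1 child is left out of the only progression table and entry into puberty is not analysed anywhere. Whether that was intended cannot be told from the documents.

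The conclusion assumes that pubertal means stage 2 or higher on the scale being tabulated. The SAP does not define the term, but Appendix 9 labels stage 1 prepubertal on every scale it gives.

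The practical size is modest and cannot be quantified. The number affected is unknown and may be small, and the result would be descriptive. The correction is still worth making before the tables are built, because it changes what the trial can report on a paediatric safety endpoint.

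**What to change.** In SAP section 4.7.1, replace the restriction to participants pubertal at baseline with all participants at Tanner stages 1 to 4 at baseline. Keep the split by sex and treatment, and use baseline stage as the rows, so that movement from stage 1 to stage 2 or higher can be read directly. Give the number at stage 5 at baseline as a separate count, because those participants are not re-staged. The 4-level category then becomes valid and the table matches the endpoint in section 1.1. If stage 1 turns out to hold very few children, a listing of them would serve.

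The cost is one sentence and a table-shell edit. It needs no new data and does not affect type I error control.
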